As a result of conducting virtual consultations and telephone calls, the following procedures will not be performed during the COVID19 pandemic, therefore have been halted as an urgent safety measure:

- BP and Pulse measurements – Participants who are known to have hypertension have home BP monitoring machines and their BP measurements are being collected and assessed by the study team during remote visits. There is no undue risk for those who do not have hypertension, as Liraglutide is not related to BP, and participants are all established on the drug.
- Bloods (lipids, renal, LFTs, thyroid, FBC & HbA1c, amylase) at V9, 11 & 13/15 only - The amylase test usually taken at visits 9, 11 & 15 is a safety blood in relation to pancreatitis. During the remote visits, all participants will be monitored for any new symptoms which will be appropriately managed by the study clinical team. The small number of participants who have diabetes will regularly check their blood glucose at home as usual. All other bloods are taken to assess efficacy, therefore not conducting them will have no impact on participant safety. All participants will be asked to report AE/SAE during remote visits.
- ACR urine test – Not conducting this poses no additional risk to participants.

Once restrictions due to the COVID19 pandemic have been lifted, a further risk assessment will be completed and in agreement with the Sponsor, Study team and NHS Host Organisations, face to face visits will be re-implemented. For the avoidance of doubt, virtual consultations will still be an option for study visits, as preferred by the participant or recommended by the study clinician, to aid the retention of participants and study visit attendance and collection of primary outcome data (via self-reported weight measurement data).

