Overall hypoglycaemia rate – ADA definition	52, 104	Hypoglycaemia events will be defined as per Appendix 5 for people without

		diabetes and as per the ADA definition in Appendix 5 for people with diabetes. Hypoglycaemia rate will be calculated per participant as total number of hypoglycaemia events divided by the total follow-up time.
Overall hypoglycaemia rate – Novo Nordisk	52, 104	Hypoglycaemia events will be defined as per Appendix 5 for people without diabetes and as per the Novo Nordisk definition in Appendix 5 for people with diabetes. Hypoglycaemia rate will be calculated per participant as total number of hypoglycaemia events divided by the total follow-up time.
AEs	Continual	Defined as in protocol with MEDRA coding used to classify AEs into System Organ Classes
SAEs	52, 104	Defined as in protocol with MEDRA coding used to classify SAEs into System Organ Classes
Rates of severe hypoglycaemia	52, 104	Calculated per participant as total number of severe hypoglycaemia events divided by the total follow-up time, where severe hypoglycaemia is defined as hypoglycaemic episodes requiring the assistance of another person to actively administer carbohydrate, glucagon, or other resuscitative actions (i.e., 'severe hypoglycaemic episodes')
Change in heart rate from baseline (beats per minute)	52, 104	Follow-up heart rate – baseline heart rate
Compliance of patient with the treatment		
Compliant with Tier 3 service (completers)	52, 104	Binary indicator of 1 if participant is compliant, 0 otherwise (defined in study database)
Stopped treatment with LIRA 3mg because of adverse effects	52, 104	Binary indicator of 1 if participant stopped treatment with LIRA 3mg because of adverse effects*, 0 otherwise. Only defined for participants in intervention arm who were currently eligible for LIRA 3mg treatment. * This includes main reason of 'adverse event' or 'unable to tolerate drug'.
The adherence of participants with the LIRA	52, 104	Participants will be defined as treatment compliant if they self-administer at least 70% of planned doses. Binary indicator of 1 if participant is compliant, 0 otherwise.

3mg (monitored through specific questionnaire and return of used pens)		Given the change in visits as a result of COVID-19 to allow face-to-face, this will be defined using the questionnaire answers as detailed in Appendix 7. Only defined for participants in intervention arm who were currently eligible for LIRA 3mg treatment.

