- A score of 3 or more is sensitive for moderate-severe OSA but is not very specific, there is a high false positive rate.
- A score of 5-8 is far more specific and indicates a high probability of moderate-severe OSA.

12 Appendix 5: Definitions of hypoglycaemia

A hypoglycaemic episode will be defined as treatment emergent if the onset of the episode is on or after the first day of randomised treatment and no later than 14 days after the last day of randomised treatment. Hypoglycaemic events will be defined as nocturnal if the time onset is between 00:01 and 05:59 (both included).

A hypoglycaemic episode form and an Adverse Event (AE) form must be filled in for all hypoglycaemic episodes. Hypoglycaemic episodes requiring the assistance of another person to actively administer carbohydrate, glucagon, or other resuscitative actions (i.e., 'severe hypoglycaemic episodes') will be qualified as an event of special interest.

A different definition of hypoglycaemia will apply for patients with type 2 diabetes and a different definition will apply for patients without diabetes.

Classification of hypoglycaemia for participants with type 2 diabetes

All participants with diabetes will be supplied with a glucose meter and a diabetes diary for recording of hypoglycaemia, symptomatic episodes and routine blood glucose monitoring. Plasma glucose should always be measured from all participants with diabetes when there is the suspicion of a hypoglycaemic episode.

All plasma glucose values ≤ 3.1 mmol/L (56mg/dL), as well as values > 3.1 mmol/L (56mg/dL) when hypoglycaemic symptoms have occurred should be recorded by the participants in the diaries. Hypoglycaemic episodes will be recorded by the participant in his/her diary throughout the trial and must be transcribed into the CRF by the Investigator at each site visit throughout the trial.

Hypoglycaemic episodes will be summarised based on the American Diabetes Association (ADA) classification and Novo Nordisk's definition.

Novo Nordisk definition

In normal physiology, hypoglycaemia symptoms occur at a blood glucose level of approximately < 2.8 mmol/L (50 mg/dL)/plasma glucose level < 3.1 mmol/L (56 mg/dL). Therefore, Novo Nordisk has used this cut-off value to define minor hypoglycaemia.

Minor hypoglycaemic episode is defined as:

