- An episode with symptoms consistent with hypoglycaemia with confirmation by plasma glucose < 3.1 mmol/L (56 mg/dL), or full blood glucose < 2.8 mmol/L (50 mg/dL) and which is handled by the subject himself/herself

- Or any asymptomatic plasma glucose value < 3.1 mmol/L (56 mg/dL) or full blood glucose value < 2.8 mmol/L (50 mg/dL). Minor hypoglycaemic episodes will be summarised according to this definition, and can be subject to additional analysis.

ADA hypoglycaemia classification

According to ADA the definition of a hypoglycaemic episode is categorised as:

Severe hypoglycaemia: An episode requiring assistance of another person to actively administer carbohydrate, glucagon, or other resuscitative actions.

Documented symptomatic hypoglycaemia: An episode during which typical symptoms of hypoglycaemia are accompanied by a measured plasma glucose concentration ≤ 3.9 mmol/L.

Asymptomatic hypoglycaemia: An episode not accompanied by typical symptoms of hypoglycaemia, but with a measured plasma glucose concentrations ≤ 3.9 mmol/L.

Probable symptomatic hypoglycaemia: An episode during which symptoms of hypoglycaemia are not accompanied by a plasma glucose determination (but that was presumably caused by a plasma glucose concentration ≤ 3.9 mmol/L).

Relative hypoglycaemia: An episode during which the participant reports any of the typical symptoms of hypoglycaemia and interprets those as indicative of hypoglycaemia, but with a measured plasma glucose concentration > 3.9 mmol/L.

Classification of hypoglycaemia for participants without diabetes

Participants without diabetes will not be routinely provided with blood glucose meters or diaries; hence blood glucose will not be measured in case of symptoms of hypoglycaemia unless it coincides with a clinic visit.

The hypoglycaemia events for participants without diabetes will be reported spontaneously i.e., symptoms of hypoglycaemia (not biochemically confirmed) occurring outside of visits to the clinic; severe hypoglycaemia will be defined as an episode requiring assistance of another person to actively administer carbohydrate, glucagon, or other resuscitative actions. In the event of severe or symptomatic hypoglycaemia patients will be given a glucose monitor and asked to record their blood glucose whenever they feel symptomatic.

13 Appendix 6: IPAQ scoring system

Further details including data processing rules can be found here:

<https://sites.google.com/site/theipaq/scoring-protocol>

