16.13 Summary of continuous safety outcomes

Outcome	Baseline		Follow-up		Change from baseline	
	Control	Intervention	Control	Intervention	Control	Intervention
Overall hypoglycaemia rate – ADA definition at 52 weeks						
Number						
Mean						
SD						
Median						
Range						
Interquartile range						
Overall hypoglycaemia rate – ADA definition at 104 weeks						
Number						
Mean						
SD						
Median						
Range						
Interquartile range						
Overall hypoglycaemia rate – Novo Nordisk definition at 52 weeks						
Number						
Mean						
SD						
Median						
Range						
Interquartile range						
Overall hypoglycaemia rate – Novo Nordisk definition at 104 weeks						
Number						
Mean						
SD						
Median						
Range						
Interquartile range						
Overall adverse event rate at 52 weeks						
Number						
Mean						
SD						
Median						
Range						
Interquartile range						

Outcome	Baseline		Follow-up		Change from baseline	
	Control	Intervention	Control	Intervention	Control	Intervention
Overall adverse event rate at 104 weeks						
Number						
Mean						
SD						
Median						
Range						
Interquartile range						
Overall serious adverse event rate at 52 weeks						
Number						
Mean						
SD						
Median						
Range						
Interquartile range						
Overall serious adverse event rate at 104 weeks						
Number						
Mean						
SD						
Median						
Range						
Interquartile range						
Overall severe hypoglycaemia event rate at 52 weeks						
Number						
Mean						
SD						
Median						
Range						
Interquartile range						
Overall severe hypoglycaemia event rate at 104 weeks						
Number						
Mean						
SD						
Median						
Range						
Interquartile range						
Heart rate (beats per minute) at 52 weeks						
Number						

Outcome	Baseline		Follow-up		Change from baseline	
	Control	Intervention	Control	Intervention	Control	Intervention
Mean						
SD						
Median						
Range						
Interquartile range						
Heart rate (beats per minute) at 104 weeks						
Number						
Mean						
SD						
Median						
Range						
Interquartile range						

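### The ADA and Novo Nordisk hypoglycaemia rates each mix two event definitions and two ways of finding events, and Table 16.13 does not split them by diabetes status

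*SAP*

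**What the plan says.** **Rate.** SAP 2.2.1 has two overall hypoglycaemia endpoints, one per classification, at 52 and 104 weeks. Both use the same formula: "Hypoglycaemia rate will be calculated per participant as total number of hypoglycaemia events divided by the total follow-up time".

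**Event definition.** Each endpoint applies a different definition according to diabetes status. The second endpoint reads: "Hypoglycaemia events will be defined as per Appendix 5 for people without diabetes and as per the Novo Nordisk definition in Appendix 5", where the latter definition covers those who have the condition. The first has the same structure, with ADA in place of Novo Nordisk.

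**Finding events.** SAP Appendix 5 states: "All participants with diabetes will be supplied with a glucose meter and a diabetes diary". For the rest: "Participants without diabetes will not be routinely provided with blood glucose meters or diaries", and "The hypoglycaemia events for participants without diabetes will be reported spontaneously i.e., symptoms of hypoglycaemia (not biochemically confirmed"). After a severe or symptomatic episode, "patients will be given a glucose monitor and asked to record their blood glucose whenever they feel symptomatic".

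**Reporting.** Safety analyses use the safety population, which is everyone randomised (SAP 3.3.5 and section 6). Table 16.13 has rows such as "Overall hypoglycaemia rate – ADA definition at 52 weeks", with columns for control and intervention only. Section 6 also tabulates hypoglycaemia events by glycaemic status for each classification, but specifies no rate or person-time.

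**Share with diabetes.** Diabetes is one of four qualifying conditions (Protocol 7.2). No percentage is given. Protocol 8.10 says only: "The small number of participants who have diabetes will regularly check their blood glucose at home as usual". Randomisation is stratified by centre and BMI (Protocol 8.3.1.1).

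**The concern.** A rate that carries the name of a classification should count events under that classification, in people in whom such events can be found. Here one figure per arm combines meter-and-diary data from one group with volunteered symptoms from another. The result depends on how many participants have diabetes as well as on how often hypoglycaemia occurs.

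The missing figure is the rate in people with diabetes. Protocol 14.10.1 names those taking sulphonylureas as possibly at higher risk, and a reader of Table 16.13 could not see the rate in the diabetes group to which they belong. Elsewhere the SAP avoids this kind of mixing: in 2.2.1, HbA1c change is calculated for each glycaemic status, and ACR is limited to the participants in whom it is measured. Protocol 10.4.1 itself places the ADA and Novo Nordisk summaries under the heading for type 2 diabetes.

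**Working it through.** The documents give no hypoglycaemia rate, event count or diabetes share, so there is no stated figure to reproduce. The check compares the definitions and then sees what averaging over an arm does.

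**1. Definitions (SAP Appendix 5)**

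| | With diabetes | Without diabetes |
|---|---|---|
| Novo Nordisk label | Minor episodes only: plasma glucose below 3.1 mmol/L (or the blood equivalent), with symptoms and self-treated, or without symptoms | Unconfirmed symptoms; severe (assisted) episodes |
| ADA label | Severe; documented symptomatic; asymptomatic at or below 3.9 mmol/L; probable symptomatic (no reading); relative | Unconfirmed symptoms; severe (assisted) episodes |

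Under Novo Nordisk the two columns count different things. Under ADA they overlap, because severe and probable symptomatic episodes need no glucose value. What differs is detection: asymptomatic low readings need a meter, and a diary prompts recording.

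**2. What the arm mean estimates**

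Let p be the share with diabetes, rD the mean rate with diabetes, rN the mean reported rate without, and k = rN/rD.

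- Arm mean of the per-participant rates = p·rD + (1 − p)·rN
- Diabetes-only rate ÷ arm mean = 1 / [p + (1 − p)·k]

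For example, p = 0.25 and k = 0.1 give 1/(0.25 + 0.075) = 3.08. All p and k below are assumptions.

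| p | k = 0 | k = 0.1 | k = 0.25 | k = 0.5 | k = 1 |
|---|---|---|---|---|---|
| 10% | 10.0 | 5.26 | 3.08 | 1.82 | 1.0 |
| 20% | 5.0 | 3.57 | 2.50 | 1.67 | 1.0 |
| 25% | 4.0 | 3.08 | 2.29 | 1.60 | 1.0 |
| 30% | 3.33 | 2.70 | 2.11 | 1.54 | 1.0 |
| 40% | 2.50 | 2.17 | 1.82 | 1.43 | 1.0 |
| 50% | 2.0 | 1.82 | 1.60 | 1.33 | 1.0 |
| 60% | 1.67 | 1.56 | 1.43 | 1.25 | 1.0 |

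The range is 1.0 to 10. On this grid, a factor of 3 or more needs p ≤ 30% with k = 0, p ≤ 25% with k = 0.1, or p = 10% with k = 0.25.

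A simulation with p = 0.25, rD = 1, rN = 0 and equal follow-up gave an arm mean of 0.255, the same as pooled events over pooled time. The mean in diabetes alone was 1.01, and the arm median was 0.

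**3. Effect on the comparison of arms**

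Assume rD = 1 in control and 1.5 in intervention (ratio 1.5, difference 0.5), with p = 0.25 in both arms.

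- rN = 0: 0.25 v 0.375. The ratio stays 1.5; the difference becomes 0.125.
- rN = 0.25: 0.4375 v 0.5625. The ratio becomes 1.29; the difference is 0.125.

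**4. Chance imbalance in diabetes share**

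Assume no drug effect, rD = 2, and shares of 35% v 25%.

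- rN = 0: 0.70/0.50 = 1.40
- rN = 0.1: 0.765/0.575 = 1.33
- rN = 0.3: 0.895/0.725 = 1.23

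With 261 and 131 participants and an overall share of 30%, the standard error of the difference in shares is √[0.30 × 0.70 × (1/261 + 1/131)] = 0.049. Ten points is therefore about 2.04 standard errors. An imbalance of about one standard error, 30% v 25% with rN = 0, gives 0.30/0.25 = 1.2.

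**The case against.** The case for leaving the plan alone has four parts.

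- **The all-participant rate was planned.** Protocol 6.4.2 lists an overall rate, and Protocol 10.4 says openly that definitions differ by diabetes status. This stands. It supports keeping an overall summary, but not giving it a classification label that fits only some participants.
- **Time without diabetes is not event-free.** Symptomatic and severe episodes count there, and a monitor follows such an episode. Some unconfirmed symptoms could also meet ADA's probable symptomatic category. This stands, and it limits the ADA point to unequal ascertainment.
- **Other outputs help.** Section 6 shows events by glycaemic status, Table 16.4 shows glycaemic status by arm, severe hypoglycaemia has its own rate, and listings are planned. A reader could divide events by group size, but not by person-time.
- **The outcome is descriptive.** No test is planned, and no primary result depends on it. This stands.

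A reader might go further and infer that the SAP divides events by everyone's follow-up and so understates the rates several-fold. The formula is per participant; the mixing arises only when individual rates are summarised over an arm. The size rests on a diabetes share and event rates that the documents do not give. A reader might also infer that a chance imbalance would pass for a drug effect. The ratio of 1.4 needs an imbalance of about two standard errors and no reported events at all without diabetes.

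**Conclusion.** The concern holds as a defect in definition and presentation. Each labelled rate combines two event definitions and two ascertainment methods, and Table 16.13 does not separate them. The mismatch in definition is clearest for Novo Nordisk; for ADA it is mainly one of detection. It would be too strong to say that the ADA figure describes ADA hypoglycaemia in nobody.

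The arm mean depends on the share with diabetes, and the rate in people with diabetes is not reported. The dilution lies between 1-fold and 10-fold over the assumed ranges, and the documents do not narrow it: calling the number with diabetes small makes a larger factor plausible but does not establish one. If diabetes shares are equal and nobody without diabetes reports events, the ratio between arms is unaffected and only the absolute difference shrinks. The change is worth making because it is cheap and makes the safety rates interpretable.

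**What to change.** In SAP 2.2.1 and Table 16.13:

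- Split the ADA and Novo Nordisk rows by baseline glycaemic status (Appendix 8). For participants with diabetes, who are supplied with a meter and diary, give events, person-time and rate by arm under each classification.
- State where the separate baseline category of diabetes remission is placed.
- Report symptom-reported episodes in participants without diabetes as their own rate with their own person-time, without either classification label. Say how readings from monitors issued during follow-up are counted.
- Keep severe hypoglycaemia for all participants, since its definition is the same in both groups.
- Add person-time to the section 6 tabulation so that the two outputs agree.

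This costs SAP wording and extra table rows, with no new data. The drawback is less precision in the smaller diabetes group.

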- Proportion of individuals with at least one AE of given severity by treatment and overall
- Proportion of individuals with at least one AE of given 'likelihood related' by treatment and overall.

For System Organ Classes with >0.1 AEs per person-year, the AEs broken down by higher level term.

Additionally, separate listings of all AEs and SAEs will be produced, including 'likelihood related', expectedness, duration, severity, action taken, outcome, and treatment, with sorting by randomisation group, participant ID, then date.

Finally, hypoglycaemia events will be tabulated by Glycaemic status for ADA and Novo Nordisk definition separately.

The safety analyses will use the safety population.

7 References

8 Appendix 1: Scoring for King's College Obesity Staging System

	Stage 0 Normal Health	Stage 1 At risk of disease	Stage 2 Established disease	Stage 3 Advanced disease
Airways	Normal	Snoring	CPAP therapy	Cor pulmonale
BMI	<35kg/m ²	35-40 kg/m ²	40-60 kg/m ²	>60 kg/m ²
Cardiovascular	<10% risk	10-20% risk	Heart disease	Heart failure
Diabetes	Normal	Impaired fasting glucose	Type 2 diabetes	Uncontrolled type 2 diabetes
Economic	Normal	Increased expense for clothes and travel	Workplace discrimination	Unemployment due to obesity
Functional	Can walk three flights of stairs	Can walk one or two flights of stairs	Requires mobility aid	Housebound
Gonadal	Normal	PCOS/erectile dysfunction	Subfertility	Sexual dysfunction leading to relationship breakdown
Health status (perceived)	Normal	Low mood or QoL	Depression or poor QoL	Severe depression
Image (body)	Normal	Dislikes body	Body image dysphoria	Eating disorder

Abbreviations: CPAP, Continuous Positive Airway Pressure; PCOS, Polycystic Ovarian Syndrome; QoL, Quality of Life.

9 Appendix 2: Scoring for PHQ-9 Questionnaire

PHQ-9* Questionnaire for Depression Scoring and Interpretation Guide

For physician use only

Scoring:

Count the number (#) of boxes checked in a column. Multiply that number by the value indicated below, then add the subtotal to produce a total score. The possible range is 0-27. Use the table below to interpret the PHQ-9 score.

Not at all	(#)	x 0 =	_____
Several days	(#)	x 1 =	_____
More than half the days	(#)	x 2 =	_____
Nearly every day	(#)	x 3 =	_____

Total score: _____

Interpreting PHQ-9 Scores

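### For participants with diabetes, the overall ADA hypoglycaemia rate, read as written, counts symptoms with glucose measured above 3.9 mmol/L, and apart from severe events no planned output separates the ADA categories

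*SAP*

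**What the plan says.** SAP 2.2.1 lists an overall hypoglycaemia rate under the ADA definition at 52 and 104 weeks. Events are taken from the rules in Appendix 5 for people without "diabetes and as per the ADA definition in Appendix 5 for people with diabetes". The derivation then reads: "Hypoglycaemia rate will be calculated per participant as total number of hypoglycaemia events divided by the total follow-up time". No category is excluded.

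Appendix 5 introduces the classification with the words "According to ADA the definition of a hypoglycaemic episode is categorised as" and lists five types: severe, documented symptomatic, asymptomatic, probable symptomatic and relative. Relative hypoglycaemia is an episode in which the participant has typical symptoms and "interprets those as indicative of hypoglycaemia, but with a measured plasma glucose concentration > 3.9 mmol/L". Protocol 10.4.3 carries the same list.

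On data capture, Appendix 5 and Protocol 10.4.1 ask participants with diabetes to record all plasma glucose values of 3.1 mmol/L or below. Values above 3.1 mmol/L "when hypoglycaemic symptoms have occurred should be recorded by the participants in the diaries". No upper limit is set.

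On reporting, Appendix 5 states: "Hypoglycaemic episodes will be summarised based on the American Diabetes Association (ADA) classification" and the Novo Nordisk definition. Table shell 16.13 has one overall ADA rate, one overall Novo Nordisk rate and one severe rate at each time point. SAP section 6 adds that "hypoglycaemia events will be tabulated by Glycaemic status for ADA and Novo Nordisk definition separately".

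**The concern.** A relative episode is one where glucose was measured and was not at or below the ADA threshold of 3.9 mmol/L. Recording such episodes is reasonable, and they belong to the classification that the trial adopted. The difficulty is that they are pooled into a figure labelled as the overall hypoglycaemia rate and cannot then be identified.

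This matters more in an open-label trial (SAP 1.2.5), because symptom reporting can depend on knowing the allocation. The intervention arm is told about side effects and has fortnightly titration reviews in weeks 0 to 8 (Protocol 8.3.1.2). Those still on LIRA 3mg also have visits at weeks 65 and 91 (Protocol 8.4.1). Diary episodes are transcribed at site visits, so the opportunity to report symptoms is not identical in the two arms. Protocol 14.10.1 also names participants with diabetes on sulphonylureas as possibly at higher risk of hypoglycaemia. They fall within the group affected here.

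**Working it through.** The plan states no hypoglycaemia count or rate, so there is no figure to reproduce. The check compares the text of SAP 2.2.1, section 6, Appendix 5 and Table 16.13, with some algebra for size.

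**Step 1: what enters the rate, and what is shown separately (participants with diabetes)**

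| ADA category in Appendix 5 | Glucose condition | In the overall ADA rate as written | Own planned output |
|---|---|---|---|
| Severe | none (assistance needed) | yes | yes: 2.2.1 and Table 16.13 |
| Documented symptomatic | measured, ≤ 3.9 mmol/L | yes | none |
| Asymptomatic | measured, ≤ 3.9 mmol/L | yes | none |
| Probable symptomatic | not measured | yes | none |
| Relative | measured, > 3.9 mmol/L | yes | none |

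**Step 2: do relative episodes reach the data?** Yes. The diary rule covers any value above 3.1 mmol/L when there are symptoms. It does not ask for symptom-free values above 3.1 and up to 3.9 mmol/L, although these meet the ADA asymptomatic category. Capture therefore leans towards symptom-driven episodes.

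**Step 3: can another output recover the split?**
- The section 6 tabulation divides events by glycaemic status and by definition. It isolates participants with diabetes but not the ADA categories.
- The Novo Nordisk rate requires plasma glucose below 3.1 mmol/L for minor episodes. The gap between it and the ADA rate mixes documented and recorded asymptomatic episodes from 3.1 to 3.9 mmol/L, probable episodes and relative episodes.
- The adverse event listing fields named in section 6 include neither glucose value nor ADA category.

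**Step 4: size.** Let r be the share of ADA events in participants with diabetes that are relative. If T is the rate in that group with all events, the rate without relative events is T(1−r). The ratio of the first to the second is 1/(1−r).
- r = 10%: 1/0.90 = 1.11
- r = 25%: 1/0.75 = 1.33
- r = 50%: 1/0.50 = 2.00

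These shares are assumptions. Because Table 16.13 averages per-participant rates, r is strictly the relative share of the summed rates, which equals the share of events when follow-up times are equal.

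The overall rate also includes participants without diabetes, who have no relative category. If a share d of all counted events comes from participants with diabetes, the factor for the whole-arm rate falls to 1/(1−d·r). With d assumed at 50%, it is 1/0.95 = 1.05, 1/0.875 = 1.14 and 1/0.75 = 1.33 for the same three values of r.

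**The case against.** The SAP never says in words that the five categories are added. The Appendix 5 sentence on summarising by the ADA classification could mean a summary by class. It stands that this is an inference from the endpoint derivation. But the derivation takes the total number of events, and no table shell carries out a summary by class beyond severe events, so an analyst following the plan would pool them.

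The effect is also narrow. Safety outcomes are tabulated without formal tests (SAP 5.8), and Protocol 8.10 describes the participants with diabetes as few. A glucose-based Novo Nordisk rate and a severe rate stand alongside. Participants with diabetes in both arms receive meters and diaries, and the nine clinical review visits apply to both arms. All of this stands and limits the importance of the point.

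Four stronger readings are tempting, but the documents do not support them:
- A reader might infer that there is no breakdown at all. Severe hypoglycaemia has its own endpoint and rows.
- A reader might infer that the rate attributes these episodes to liraglutide. It attributes nothing. Relatedness is recorded and reported separately.
- A reader might infer a specific false difference between arms. With equal rates apart from relative episodes, shares of 30% and 10% would give 0.9/0.7 = 1.29. Those shares have no basis in the documents, and Table 16.13 plans no ratio for this endpoint. Table 16.15 has a ratio column for hypoglycaemia as an expected adverse event, but not on the ADA classification.
- A reader might infer that probable symptomatic episodes should also leave the main rate. In those episodes no glucose was taken, so nothing contradicts hypoglycaemia. Dropping them from a safety rate is debatable and does not follow from the argument about relative episodes.

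**Conclusion.** The point holds in limited form. For participants with diabetes, the overall ADA rate as written includes episodes with glucose measured above 3.9 mmol/L. Apart from severe events, no planned output breaks the count down by ADA category. The reported rate therefore cannot support a statement about confirmed ADA episodes, and the Novo Nordisk rate does not fill the gap.

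The size is unknown, because it depends wholly on the share of relative episodes. The factors in the working show the form of the effect and are not predictions. The primary outcome and the tested anthropometric outcomes are not touched. The conclusion rests on reading the total in SAP 2.2.1 literally. If the sponsor intends something else, the SAP should say so.

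**What to change.** 1. In Table 16.13, for participants with diabetes, add event counts and rates by arm at 52 and 104 weeks for each of the five Appendix 5 categories.
2. In SAP 2.2.1, state that the overall ADA rate will be shown with and without relative episodes. Keep probable symptomatic episodes in both versions, with their own row.

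This changes reporting only. The classification and the clinical handling of episodes stay as they are. The cost is two sentences and one extra table with small cell counts. The diary entries are to be transcribed into the CRF. The fields of the hypoglycaemia form are not in the documents, so the trial team should confirm that glucose value and symptoms can be retrieved for each episode. The SAP is marked version 1.1 DRAFT and its introduction says that it will be finalised before database lock, so the change fits there if lock has not yet taken place.
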